#### 4.3.6 Per protocol set of patients

This set will be composed of all patients of the FAS free from major protocol deviation, which can bias the estimate of the treatment effect. Patients with major deviations will be listed during the Blind Data Review Meetings and the reason for exclusion will be provided. Post-treatment biopsy evaluable for efficacy not available will be considered as a major protocol deviation.

The figure below summarizes the patient populations to be considered:

Note:

When considering actual treatment received:

- if a patient received both active and placebo IMPs during the study, active IMP will be considered as actual treatment

- if a patient received active IMP at both doses (800 mg and 1200 mg) during the study due to dispensation error(s), the dose of 1200 mg will be considered as actual treatment

#### 4.4 Protocol deviations (PDs)

The list of PDs has already been developed (see Excel file appended to BDRM minutes named “INVEN\_21507\_Native\_Deviation”).

All PDs will be carefully identified through eCRF data before the BDRMs. During the BDRMs held before database lock (DBL), each PD will be classified as leading to exclusion from the PP population (“major”) or not leading to exclusion from the PP population (“minor”).

All PDs related to study inclusion or non-inclusion criteria, conduct of the trial, patient management or patient assessment will be described, such as:

- Violation of inclusion criteria
- Violation of exclusion criteria
- Intake of non-allowed concomitant medications during the treatment period
- Randomisation error
- Lack of compliance
- Primary endpoint not assessable (missing post-treatment biopsy results)
- Etc.

Additionally, the PDs that could not be identified through eCRF data will also be reviewed during the BDRMs. This listing will be based on the PD forms completed by the study monitors. These PDs will be extracted from the listing and imported in the database.

## 4.5 Derived variables

### 4.5.1 Baseline data and change from baseline

Baseline data will be considered as the last available non-missing data before or equal to the treatment start.

*Note: For biopsies, multiple reading rules (see section 4.5.4.1.1) should be applied before calculating Baseline values.*

Absolute change from baseline will be calculated as follows:

Value at  $V_i$  – Value at baseline, where  $i$  corresponds to a post-baseline value.

Relative change from baseline (in %) will be calculated as follows:

- if Value at baseline is not equal to 0:  $[(\text{Value at } V_i - \text{Value baseline}) / \text{Value at baseline}] * 100$ , where  $i$  corresponds to a post-baseline value.
- if both values at  $V_i$  and at baseline are equal to 0, then the relative change from baseline will be equal to 0%.

Regarding laboratory parameters that are sensitive to the fasting status (Fasting Glucose, HOMA, insulin, C-peptid, Fructosamine, Triglycerides, Total cholesterol, HDL cholesterol, LDL cholesterol, Free fatty acids (FFA), Apoprotein A1, Apoprotein B, Apoprotein C3, Adiponectin, Leptin, FGF-21):

- if the value at Baseline is a non-fasting value when the value at Screening is a fasting value, then the Baseline data will be the value at Screening
- if both values at Screening and Baseline are non-fasting values, then the Baseline data will be the value at Baseline.

Regarding laboratory parameters, the following status will be defined:

- Normal-Normal, if the baseline is within laboratory ranges and all values over time remain within laboratory ranges
- Normal-Abnormal, if the baseline is within laboratory ranges but at least one value over time is not within laboratory ranges
- Abnormal-Normal, if the baseline is not within laboratory ranges and all values over time are within laboratory ranges
- Abnormal-Abnormal, if the baseline is not within laboratory ranges and at least one value over time is not within laboratory ranges

### 4.5.2 Disposition data

#### - **Visit performed**

A visit will be considered as performed, if a visit date is reported for this visit.

#### - **Patient still under treatment, if visit performed**

A patient will be considered as “still under treatment” at a given visit if last treatment intake is  $\geq$  visit date - 3.

- **Patient still ongoing, if visit NOT performed**

A patient will be considered as “still ongoing” at a given theoretical visit if another visit has been performed after this missing one.

- **Patient still under treatment, if visit NOT performed**

A patient will be considered as “still under treatment” at a given theoretical visit if last treatment intake is  $\geq$  theoretical visit date - 3.

- **Study duration (months)**

Study duration (in months) is defined as the time between the randomisation date and the date of End of Study:  $(\text{Date of End of Study} - \text{randomisation date} + 1) / 30.4375$ .

- **Study duration (weeks)**

Study duration (in weeks) is defined as the time between the randomisation date and the date of End of Study:  $(\text{Date of End of Study} - \text{randomisation date} + 1) * 52 / 365.25$ .

- **Premature treatment withdrawal**

A patient will be considered as having prematurely discontinued study treatment if the reason for end of treatment is different from “Treatment period terminated as per protocol”.

- **Completer patients**

A patient will be considered as a completer if he/she did not prematurely withdrawn treatment.

### 4.5.3 Baseline characteristics

#### - **Age**

Age (in years) is the one reported in the eCRF.

Patients could be classified in 2 categories according to their age:

- <65, ≥65 years old

#### - **Body Mass Index (kg/m^2)**

Body Mass Index (BMI) is equal to the ratio between the weight (in kg) and the square of the height (in meter).

Patients will be classified in 6 categories according to their BMI:

- Underweight: BMI < 18.5 kg/m^2
- Normal: BMI in [18.5 - 25[ kg/m^2
- Overweight: BMI in [25 - 30[ kg/m^2
- Obese class I (moderate): BMI in [30 - 35[ kg/m^2
- Obese class II (severe): BMI in [35 - 40[ kg/m^2
- Obese class III (morbid): BMI ≥ 40 kg/m^2

They will also be classified in 2 categories according to their BMI:

- Non-obese: BMI < 30 kg/m^2
- Obese: BMI ≥ 30 kg/m^2

#### - **Metabolic Syndrome at Baseline**

A patient will be considered as presenting a metabolic syndrome at Baseline when at least 3 of these parameters are verified (see Reference 1):

- Waist circumference ≥ 94 cm/37 inches in men, ≥ 80 cm/31.5 inches in females
- ‘Hypertension’ reported in Medical History and ticked as ‘ongoing’
  - o HYPERTENSION (MedDRA PT code=10020772),
  - o DIASTOLIC HYPERTENSION (MedDRA PT code=10012758),
  - o ESSENTIAL HYPERTENSION (MedDRA PT code=10015488)
- Pre-diabetic/diabetic condition: Actual ‘Type 2 diabetes mellitus’=Presence or **Fasting** glucose ≥ 100 mg/dl (5.6 mmol/L) if ‘Type 2 diabetes mellitus’=Absence
- Serum triglycerides > 150 mg/dL (i.e. 1.7 mmol/L) or corresponding Medical History reported
  - o HYPERTRIGLYCERIDEMIA (MedDRA PT code=10020869),
  - o FAMILIAL HYPERTRIGLYCERIDEMIA (MedDRA PT code=10059183),
  - o HYPERLIPIDAEMIA (MedDRA PT code=10062060),
  - o DYSLIPIDAEMIA (MedDRA PT code=10058108)
- HDL cholesterol < 40 mg/dL (i.e. 1.0 mmol/L) in men, < 50 mg/dL (i.e. 1.3 mmol/L) in females

- **Insulin-resistant status**

- Insulin-resistant: Actual ‘Type 2 diabetes mellitus’=Presence or **Fasting** glucose  $\geq$  100 mg/dl (5.6 mmol/L) if ‘Type 2 diabetes mellitus’=Absence
- Non insulin-resistant: **Fasting** glucose  $<$  100 mg/dl (5.6 mmol/L) and ‘Type 2 diabetes mellitus’=Absence

- **Prior medication**

A prior medication corresponds to any medication reported in the “PREVIOUS AND CONCOMITANT MEDICATIONS” form of the eCRF with an end date  $<$  first treatment intake date (after application of missing dates replacement rules, see section 4.1.6.2)

- **Concomitant medication**

A concomitant medication corresponds to any medication reported in the “PREVIOUS AND CONCOMITANT MEDICATIONS” form of the eCRF with a {start date  $\leq$  first treatment intake date and an end date  $\geq$  first treatment intake date or ongoing} or with a {first treatment intake date  $\leq$  start date  $\leq$  last treatment intake date} (after application of missing dates replacement rules, see section 4.1.6.2)

- **Antidiabetic treatment**

Four antidiabetic classes will be defined:

- o Metformin
  - CMDECOD in ("METFORMIN HYDROCHLORIDE" "METFORMIN" "METFORMIN EMBONATE" "DAPAGLIFLOZIN PROPANEDIOL MONOHYDRATE W/METFORMIN" "EMPAGLIFLOZIN W/METFORMIN HYDROCHLORIDE" "EUCREAS" "JENTADUETO" "KOMBIGLYZE" "RISTFOR")
- o Sulphonylurea
  - WHODDrug ATC code = A10BB
- o DPP4i
  - WHODDrug ATC code = A10BH or CMDECOD in ("EUCREAS" "JENTADUETO" "KOMBIGLYZE" "RISTFOR")
- o SGLT2
  - CMDECOD in ("DAPAGLIFLOZIN PROPANEDIOL MONOHYDRATE" "CANAGLIFLOZIN" "DAPAGLIFLOZIN PROPANEDIOL MONOHYDRATE W/METFORMIN" "EMPAGLIFLOZIN W/METFORMIN HYDROCHLORIDE" "DAPAGLIFLOZIN")

A patient will be considered as taking at least one antidiabetic treatment if at least one treatment detailed above is received.

- **Statins**

- HMG-CoA reductase inhibitors (WHODDrug ATC code: C10AA)

- HMG-CoA reductase inhibitors in combination with other lipid modifying agents (WHODDrug ATC code: C10BA)
  
- **Time between screening biopsy and randomisation (months)**

Time between screening biopsy and randomisation (in months) is defined as the time between the date of screening biopsy and the date of randomisation:  $(\text{Date of randomisation} - \text{date of screening biopsy} + 1) / 30.4375$

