##### *Type 2 diabetes:*

- Metformin,
- Dipeptidyl peptidase-4 inhibitors,
- Sodium-glucose transport protein 2 inhibitors: canagliflozin, dapagliflozin and empagliflozin.

Minor modification of anti-diabetic treatments or dosages are allowed if done in the context of stable type 2 diabetes, i.e. HbA1c  $\leq$ 8.5% in the previous 6 months.

**Hyperlipidemia:** only statins at stable doses within the past 3 months before pre-study treatment biopsy will be allowed.

**Antiplatelets agents:** The antiplatelets agents (incl. low-dose aspirin, ticlopidine, clopidogrel, prasugrel, ticagrelor) are allowed.

**Herbal supplements and Others Supplementation:** Herbal preparations or vitamin supplements with no exact composition known should not be started during the course of the study as they could be liver toxic.

- **Other Medications**

Medications other than the IMP and those mentioned above should only be started during the course of the study with the agreement of the Investigator in order to avoid interference with study assessments. The need for other medication may lead to exclusion of the patient from the study.

If symptomatic medication is needed to treat adverse events related to IMP, the Investigator will inform the Sponsor about the concomitant medication given.

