#### - **Treatment used for the underlying medical condition**

Treatments are allowed within certain restrictions (described above and below) and provided they have been kept at **stable doses for at least 6 months before the pre-treatment biopsy.**

- *Type 2 diabetes*: Metformin is allowed as well as dipeptidyl peptidase-4 inhibitors and sodium-glucose transport protein 2 inhibitors: canagliflozin, dapagliflozin and empagliflozin. Glucagon like peptide-1 receptor agonists (liraglutide, exenatide) or glitazones are not allowed
- *Hyperlipidemia*: only statins at stable doses will be allowed
- *Antiplatelets agents*: The antiplatelets agents (aspirin, ticlopidine, clopidogrel, prasugrel, ticagrelor) are allowed
- *Herbal supplements and Others Supplementation*: Herbal preparations or vitamin supplements should not be taken as it is difficult to know exactly what they contain and could be liver toxic

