#### 5.1.12 *Concomitant medications*

The number (%) of patients with at least one concomitant medication will be presented and corresponding medications will be described by Medication Class (ATC2 levels) and Medication Name in the FAS.

The analysis will be done on all concomitant medications in a first time. Then it will be repeated on the following treatments of interest:

- Antidiabetic treatments administered, see section 4.5.3.
- Statin treatments administered, see section 4.5.3.

The number (%) of patients with at least one concomitant medication will be presented overall (all antidiabetic treatments) and for each antidiabetic treatment of interest and for each statin treatment.

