### 5.2.3.8 *Glucose metabolism*

#### **Main analysis**

The population of analysis will be the FAS as described in section 4.3.3. Only the observed cases under treatment will be analysed (see section 4.1.6.3).

Only fasting results will be considered for fasting glucose, insulin, C-peptid and HOMA index. HbA1c and fructosamide results will be considered regardless of the fasting status.

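### The SAP's SGLT2 drug list omits single-agent empagliflozin, which the protocol allows, and no specified table separates antidiabetics held at first dose from those started later

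*SAP*

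**What the plan says.** Protocol 4.2.4 names the drugs allowed for type 2 diabetes: metformin, DPP-4 inhibitors, and "Sodium-glucose transport protein 2 inhibitors: canagliflozin, dapagliflozin and empagliflozin". SAP 3.4.4 repeats the same three SGLT2 inhibitors and adds that "Glucagon like peptide-1 receptor agonists (liraglutide, exenatide) or glitazones are not allowed". Insulin is on the prohibited list in protocol 4.2.3, and type 2 patients on insulin are excluded at entry (exclusion criterion 11).

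In SAP 4.5.3, under Antidiabetic treatment, "Four antidiabetic classes will be defined": metformin, sulphonylurea, DPP4i and SGLT2. Sulphonylureas are captured by an ATC code, and DPP-4 inhibitors by an ATC code plus four product names. SGLT2 has no class code, only coded names: "CMDECOD in ('DAPAGLIFLOZIN PROPANEDIOL MONOHYDRATE' 'CANAGLIFLOZIN' 'DAPAGLIFLOZIN PROPANEDIOL MONOHYDRATE W/METFORMIN' 'EMPAGLIFLOZIN W/METFORMIN HYDROCHLORIDE' 'DAPAGLIFLOZIN". The overall variable is built on those four classes alone: "A patient will be considered as taking at least one antidiabetic treatment if at least one treatment detailed above is received".

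SAP 5.1.12 first tabulates all concomitant medications by ATC2 class and medication name. It then repeats the table for antidiabetics, where the number of patients "will be presented overall (all antidiabetic treatments) and for each antidiabetic treatment of interest". SAP 4.1.4 makes descriptive tables by treatment group.

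A medication is concomitant (SAP 4.5.3) if it was being taken at first intake, or if it started between first and last intake. SAP 4.1.6.2 sets an entirely missing start date to the day of first intake.

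For the glucose endpoints, SAP 5.2.3.8 states: "Only the observed cases under treatment will be analysed (see section 4.1.6.3"). Fasting glucose, HbA1c, insulin and HOMA are compared with placebo by MMRM with the Hochberg procedure. The sensitivity analysis for that section is given as none.

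**The concern.** There are two separate weaknesses.

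The first is a coding gap. The protocol allows a drug by name, and the SAP's list for that drug's class does not contain it as a single agent. The row described as covering all antidiabetic treatments then covers only what is on the list, so it can disagree, without explanation, with the general medication table in the same section.

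The second is that the table cannot distinguish background treatment from treatment added on study. Changes are foreseeable: protocol 4.2.4 permits minor modifications of antidiabetic treatment or dosage in stable diabetes, and other medication may be started with the investigator's agreement. The observed-cases-under-treatment rule in SAP 4.1.6.3 drops values collected more than 3 days after the last study-drug intake. It does not drop values collected after another glucose-lowering drug was added. A reader of the HbA1c and fasting glucose comparisons would want to know whether new starts differed between arms, and the specified tables do not say.

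**Working it through.** The plan gives no figure to reproduce here. The check applies the SAP's two written rules literally.

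**Step 1: match drug names to the coded lists in SAP 4.5.3.**

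| Drug, single agent | On a coded-name list? | Status in the documents |
|---|---|---|
| Metformin | yes | allowed |
| Canagliflozin | yes | allowed |
| Dapagliflozin | yes | allowed |
| Empagliflozin | **no** (only with metformin) | allowed |
| Insulin | no | prohibited |
| Liraglutide, exenatide | no | prohibited |
| Pioglitazone | no | prohibited (glitazone) |

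Among the drugs tested, empagliflozin is the only one that is allowed and yet unlisted.

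**Step 2: what happens to an empagliflozin patient.**

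- Empagliflozin plus separately coded metformin: missed in the SGLT2 row, still counted in the overall row through metformin.
- Empagliflozin with no other listed drug: missed in both rows.

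**Step 3: possible size.** SAP 3.5 reports 247 randomised. I assume equal arms and a FAS close to the randomised set, so 247/3 ≈ 82 per arm. If k patients in an arm took empagliflozin and no other listed drug, that arm's overall percentage is too low by 100 × k/(247/3) points:

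- k = 0: 0 points
- k = 1: 1.2 points
- k = 3: 3.6 points
- k = 5: 6.1 points

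The documents give no value for k. SAP 5.1 also calls for these tables by diabetic status. Within the diabetic stratum the denominator is smaller, so each missed patient weighs more.

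**Step 4: apply the concomitant rule.** Put first intake at day 0 and last intake at day 24 × 7 = 168. A drug counts if (start ≤ 0 and end ≥ 0 or ongoing) or (0 ≤ start ≤ 168).

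- Held before day 0 and ongoing: counted.
- Held before day 0, stopped day 1: counted.
- Started day 60: counted, in the same cell as the two above.
- Started day 170: not counted.
- Ended before day 0: not counted.

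The third case is a new start on study, and the table cannot tell it from the first.

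**Step 5: effect of date imputation.** Under SAP 4.1.6.2, a wholly missing start date becomes the day of first intake. So does a date known only to the year, if that is the year of first dose. Such a drug may have been held for years or started at week 10. Any split by start date must therefore show how many starts were imputed.

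**Step 6: where else the drugs appear.** The general table in 5.1.12 lists every medication by ATC2 class and name, by arm. The SAP's own codes for sulphonylureas (A10BB) and DPP-4 inhibitors (A10BH) share the stem A10, so an A10 row by arm is to be expected there. Non-allowed medication is described as a protocol deviation (SAP 4.4), summarised by arm and type (5.1.2), and forbidden concomitant treatment is a summarised reason for discontinuation (5.1.1). None of these is specified with a split by start date.

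**The case against.** The strongest reply is that nothing is shown to be wrong. The SAP is dated July 2020 and already reports final randomisation numbers. Its list holds brand names and salt forms, and a sulphonylurea class that the protocol does not name as allowed. It looks as if it was built from terms already coded in the database, in which case nobody may have been on single-agent empagliflozin. That is plausible, but the SAP does not say so, and the rule should be right as written. What stands is that a reader who infers that the antidiabetic table is in error goes further than the documents allow. It is in error only if at least one such patient exists.

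Second, a reader might take this as the only by-arm view of background glucose-lowering treatment, and the absence of insulin, GLP-1 agonists and glitazones as hiding their use. The documents do not support that. Those drugs are prohibited, would appear by name and arm in the all-medication table, and would be handled as deviations. The remaining defect is the label: a row said to cover all antidiabetics covers four classes.

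Third, a reader might infer that rescue treatment in the placebo arm dilutes the HbA1c difference. The documents define no glycaemic rescue pathway and give neither a rate of new starts nor a drug effect, so any amount would be the product of two assumptions. Correcting a descriptive table would not change that estimate either. Keeping values after a permitted background change is a legitimate choice.

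Finally, the table shells are a separate file that was not available. A dated listing may exist there, so the gap is established for the tables the SAP text specifies and not for the whole report.

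**Conclusion.** The point holds in a limited form. As written, SAP 4.5.3 misclassifies any patient on single-agent empagliflozin in the SGLT2 row, and also in the overall row if no other listed drug is taken. The number affected is unknown and may be zero. Under the equal-arm assumption, each patient missed by the overall row is worth about 1.2 percentage points of an arm. The overall row is also narrower than its label.

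Independently of any drug list, the concomitant definition makes new antidiabetic starts by arm unreadable from the specified tables. That matters for interpreting HbA1c and fasting glucose, which are tested without a sensitivity analysis.

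The issue is descriptive. The antidiabetic variable feeds no analysis population, no subgroup in SAP 4.7, no hypothesis test and no alpha, and the primary endpoint is untouched. The correction is worth making because it is specific and nearly free: if no such patient exists, completing the list changes no count.

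**What to change.** 1. In SAP 4.5.3, define the SGLT2 class by class code, as is done for sulphonylureas and DPP-4 inhibitors, or add single-agent empagliflozin to the coded names.
2. Add an 'other antidiabetic' row for any remaining coded glucose-lowering drug, and base the overall variable on all rows, so that the label and the content agree.
3. In SAP 5.1.12, split each antidiabetic row by arm into drugs ongoing at first dose and drugs started after first dose. State which side a start on the day of first intake falls, and show the number of imputed start dates. Limit the split to starts: the documents do not show that dose increases are captured in usable form.

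The cost is a few lines of derivation on medication data that are already coded, and one longer table. No planned analysis changes.

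Optional, and not part of the correction: a supplementary MMRM for HbA1c and fasting glucose that leaves out values after a new start. It addresses a different question, because it conditions on a post-randomisation event, and would need to be labelled so. It should not extend to insulin or HOMA, which are measured only at weeks 0 and 24, so the exclusion would remove a patient's only post-baseline value.

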#### 4.5.4 Efficacy

##### 4.5.4.1 Liver biopsy

###### 4.5.4.1.1 Multiple reading at Baseline or V3

In case of multiple reading for a given biopsy at Baseline or at V3, the following strategy needs to be applied:

- If unreadable assessment : choose readable one
- If all are unreadable, the biopsy results will be considered as missing
- If more than 1 readable assessment :
  - o Choose the worst case scenario based on the SAF-A score
  - o If both SAF-A scores are similar:
    - Choose the worst scenario based on the SAF-F score
    - If both SAF-F scores are similar:
      - Choose the last reading based on reading date

###### 4.5.4.1.2 Biopsy not performed as an efficacy endpoint

Some patients have underwent biopsies during the study that cannot be considered as the biopsies to be analysed for efficacy. These biopsies were identified during data cleaning process, and were actually reported as ‘unscheduled’ biopsies in the clinical database, in order to differentiate them with the biopsies evaluable for efficacy, reported at Visit 3 (week 24).

